3.2 Calculation of the PK variables

The following PK analysis variables will be calculated as the data handle procedures described above (section 3.1). If 2 draws of the PK at time 0 were done, the average of two will be used for time 0.

3.2.1 C_{Max}

C_{Max} is defined as the maximum concentration of G-Pen Glucagon after time 0 minute.

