## 6.2. Non-Clinical Pharmacology and Toxicology Experience with Glucagon

Native glucagon for injection (bovine, porcine origin) was approved for use in humans in 1960 [FDA CDER #1]. The 29 amino acid sequence of pancreatic glucagon is identical in humans, cows, pigs, dogs, and rats, and is also conserved in biosynthetic versions of glucagon [Eistrup]. Glucagon for injection (rDNA origin) was approved in 1998, and is currently the subject of two approved NDAs ([NDA 20-928] and [NDA 20-918]). Complete NDA-required pharmacology and toxicology data have been reviewed and accepted by the FDA, as described in Lilly Glucagon [rDNA origin] for injection and Novo GlucaGen® (glucagon [rDNA origin] for injection) labeling [Glucagon, Glucagen]. As Xeris' drug product is produced by solid-phase

peptide synthesis (SPPS), which also conserves the glucagon peptide sequence, the rDNA glucagon information is pertinent to the development of G-Pen™ (glucagon injection) for the treatment of severe hypoglycemia. A summary of this information can be found in Xeris' current Investigator's Brochure, which will be provided to each investigator participating in this study.

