#### **10.2.1. Treatment Visit 1 (Day 0)**

The following procedures will be carried out at this visit.

1. The subject will be asked about any severe hypoglycemic events (requiring the assistance of another person) since the screening visit.

- a. If a severe hypoglycemic event has occurred in the 2 weeks prior to the admission, the visit will be postponed until it has been at least 2 weeks since the last severe hypoglycemic event.
2. If it has been more than 30 days since the Screening Visit, venous blood will be collected for a repeat of baseline hematology and serum chemistry assessments. However, the treatment visit may continue based upon qualification at the Screening Visit.
3. The subject will be questioned and any changes in concomitant medications will be documented in the CRF.
4. For females of child-bearing potential, a urine pregnancy test will be performed
  - a. If positive, the subject will be discontinued from the study.
  - b. Full vital signs, including triplicate BP, will be assessed after a 5-minute seated rest. Heart rate and single BP will be repeated immediately prior to dosing and at 30, 60, 120 and 180 minutes post, with  $\pm$  10 minutes per collection time point.
5. Insertion of intravenous catheter for blood sampling.
  - a. Starting plasma glucose level will be assessed:
    - i. If  $>300$  mg/dL, ketones will be checked
    - ii. If ketones are found to be moderate or greater, the visit will be postponed.
6. Optional placement of a CGM for assessment of glucose levels during the induction phase.
  - a. If used, the CGM will be calibrated against glucose measurements obtained from the point-of-care, rapid glucose analyzer.
7. Insulin infusion will be started as described in Section 7.2.
  - a. Those subjects using injection therapy will have a second intravenous catheter inserted in the other arm for insulin infusion.
  - b. Plasma glucose levels will be measured no more than 10 minutes apart while the plasma glucose level is  $\geq 100$  mg/dL and no more than 5 minutes apart when the plasma glucose level is  $< 100$  mg/dL.
8. Once an initial plasma glucose measurement  $< 80$  mg/dL is achieved,
  - a. The basal rate will be returned to normal for subjects using an insulin pump and the insulin infusion will be stopped for subjects using insulin injections.
  - b. A first baseline PK blood sample should be collected at the point that plasma glucose first reaches a concentration  $< 80$  mg/dL.

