9. After 5 minutes, a confirmatory plasma glucose measurement will be performed.
  - a. If plasma glucose remains  $< 80$  mg/dL, collect a second baseline PK blood sample, and begin administration of the study drug (see Section 9.3.2).
  - b. If plasma glucose has risen to  $\geq 80$  mg/dL, return to step 7b and repeat the process.
10. Following study dosing, plasma glucose will be measured every  $5 \pm 2$  minutes until 90 minutes post-dosing.

11. Additional blood samples will be collected at 10, 20, 30, 45, 60, 90, 120, and 180 minutes post-dosing, with  $\pm 5$  minutes per collection, and processed and stored at  $-80 \pm 20$  C for determination of plasma glucagon levels.
12. After completing all collections and procedures at 180 minutes post-dosing, the subject will be given a meal as per the standard practice at each site, and their usual dose of insulin. The subject can then leave the clinic after plasma glucose is confirmed to be between 70 and 180 mg/dL.
13. Local tolerability will be assessed as follows:
  - a. Subjects will complete age-appropriate questionnaires regarding injection site discomfort ([Appendix 1](#)) at  $10 \pm 5$  and  $30 \pm 5$  minutes post-dosing, and again at  $180 \pm 5$  minutes post-dosing if the FPS score reported at 30 minutes is  $> 0$ .
  - b. An investigator will use the modified Draize scales ([Appendix 2](#)) to assess erythema and edema formation at the injection site at  $10 \pm 5$  and  $30 \pm 5$  minutes following administration. Any injection site with a score  $> 0$  for either erythema or edema at 30 minutes post-dosing will be re-evaluated for both at  $180 \pm 5$  minutes post-dosing.
14. Adverse events reported by the subject or observed by an investigator will be recorded in Advantage eClinical and managed as medically appropriate.

If a subject exhibits signs of distress at any time post-dosing or if plasma glucose drops below  $< 70$  mg/dL, glucose tablets may be given at the discretion of the investigator. Signs and symptoms should be monitored and if the subject's condition fails to improve within 15 minutes, additional glucose tablets or other intervention (e.g., IV dextrose) may be given at the discretion of the investigator. Every attempt should be made to complete all remaining safety and efficacy evaluations, to the extent this can be done while safeguarding the subject.

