2.4.2 Pharmacodynamic Endpoints

In the 12.0-<18.0 year-old age group, the plasma glucose change from baseline to 30 minutes after administration of G-Pen™ at a dose of 0.5 mg will be evaluated using the same approach described in Section 2.3.1 (Table 8).

Time for plasma glucose to increase by ≥ 25 mg/dL from baseline, maximum glucose concentration (C_{max}) between 0 and 90 min, the time to maximum concentration (T_{max}) will be directly obtained from the observed glucose concentration-time profile. If two identical values are recorded for C_{max} , the first one will be used for T_{max} . The area under the curve from 0 to 90 min (AUC_{0-90m}) of glucose will be calculated as the sum of areas of trapezoids, which are composed of adjacent glucose values. The following rules will be considered:

1. If there are missing data points before the last observed value, they will not be imputed.
2. If there are missing data points after the last observed value, they will be extrapolated using the last two data points.

Baseline-adjusted AUC_{0-90m} with negative values set at 0 will also be calculated. All PD endpoints will be analyzed descriptively for each age group (Table 9) and by treatment dose for subjects aged 12.0-<18.0 (Table 10). Actual time instead of protocol time will be used for calculating the time for plasma glucose to increase by ≥ 25 mg/dL from baseline, T_{max} , AUC_{0-90m} , and baseline-adjusted AUC_{0-90m} . In addition, plasma glucose concentration-time profile by age group (Figure 2 and Table 11) and by treatment dose for subjects aged 12.0-<18.0 (Figure 3 and Table 11) will be presented.

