3.1 Handling of the missing values

The PK samples are drawn blood at -5, 0, 10, 20, 30, 45, 60, 90, 120, and 180 minutes post dose, with ± 2 minutes per collection for the samples from -5 and 0 minutes, and ± 5 minutes for later samples. The following procedures will be applied to handle any missing values of the PK:

- If PK at time 0 minute (T_0) is missing, then PK at -5 minute will be substituted. If both -5 minute and 0 minute PK are missing, then the PK at later minutes will be used to impute the PK at 0 minute. In such case, linear imputation will be used.
- If PK at 120 minute is missing, then cubic imputation will be used to impute the PK at 120 minute. Exception: if PK at 120 minute is missing and the last available PK is the C_{max} , i.e., PK never comes down, and then no imputation will be done.
- All other missing PK values will not be imputed

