3.2.2 T_{Max}

T_{Max} is defined as time (min) when maximum concentration of G-Pen Glucagon reached after T_0 . If there are multiple C_{Max} following the injection, T_{Max} will be the first time when C_{Max} is reached. Actual time instead of protocol time will be used.

3.2.3 $AUC_{0-120min}$

$AUC_{0-120min}$ is calculated using Trapezoidal rule from T_0 to T_{120} . Actual time instead of protocol time will be used.

4 Statistical Analysis

The three PK variables defined in section 3.2 will be analyzed descriptive for the age groups and doses (2.0-<6.0yr 0.5mg, 6.0-<12.0yr 0.5mg, 12.0-<18.0yr 1mg, and 12.0-<18.0yr 0.5mg). Mean, standard deviation, median, minimum and maximum will be presented.

Individual figures of each subject each dose will be presented. Mean G-Pen Glucagon vs protocol time point will be presented for each age group and doses. Protocol time point will be used to allow aggregation.

5 Planned Output Table of Content

Tables	14.2.1.1	Glucagon : Cmax by age and dose
	14.2.1.2	Glucagon : Tmax by age and dose
	14.2.1.3	Glucagon : AUC0-120 by age and dose
Listing	16.2.5.1	PK profile for each subject
	16.2.5.2	PK Cmax, Tmax, AUC for each subject
Figure	14.4.1.1.subjid	Individual Glucagon profile of each subject
	14.4.1.2	average Glucagon vs time for each age group and dose

6 Mock-ups Tables/Listings/Figures
Table 14.2.1.1 Glucagon: Cmax by age and dose

CATEGORY	Glucagon: Cmax			
	2-6yr 0.5mg	6-12yr 0.5mg	12-18yr 1mg	12-18yr 0.5mg
N	6	6	6	6
Mean (SD)	x.x (x.xx)	x.x (x.xx)	x.x (x.xx)	x.x (x.xx)
Min, Median, Max	x.x (x.xx)	x.x (x.xx)	x.x (x.xx)	x.x (x.xx)

Table 14.2.1.2 Glucagon: Tmax by age and dose

CATEGORY	Glucagon: Tmax			
	2-6yr 0.5mg	6-12yr 0.5mg	12-18yr 1mg	12-18yr 0.5mg
N	6	6	6	6
Mean (SD)	x.x (x.xx)	x.x (x.xx)	x.x (x.xx)	x.x (x.xx)
Min, Median, Max	x.x (x.xx)	x.x (x.xx)	x.x (x.xx)	x.x (x.xx)

Table 14.2.1.3 Glucagon: AUC0-120 by age and dose

CATEGORY	Glucagon: Auc0-120			
	2-6yr 0.5mg	6-12yr 0.5mg	12-18yr 1mg	12-18yr 0.5mg
N	6	6	6	6
Mean (SD)	x.x (x.xx)	x.x (x.xx)	x.x (x.xx)	x.x (x.xx)
Min, Median, Max	x.x (x.xx)	x.x (x.xx)	x.x (x.xx)	x.x (x.xx)

Listing 16.2.5.1 Glucagon of each subject

PATIENT ID	Actual Date/Time	Protocol Time	Glucagon
xxxx	xx/xx/yyyy xx:xx	-5	xx
xxxx	xx/xx/yyyy xx:xx	0	xx
xxxx	xx/xx/yyyy xx:xx	10	xx
xxxx	xx/xx/yyyy xx:xx	20	xx

Listing 16.2.5.2 Glucagon Cmax, TMax, AUC of each subject

PATIENT ID	CMax	TMax	AUC01-20
XXXX	XX	XX	XX
XXXX	XX	XX	XX
XXXX	XX	XX	XX
XXXX	XX	XX	XX

[figure not shown]

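### Glucagon Cmax and AUC0-120 are defined as G-Pen exposure but computed from total glucagon; baseline-corrected values should be added beside the raw ones

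*SAP*

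**What the plan says.** SAP Appendix II, section 2, lists Cmax, Tmax and AUC0-120 as properties of G-Pen glucagon. Section 3.2.1 says that Cmax "is defined as the maximum concentration of G-Pen Glucagon after time 0 minute". Section 3.2.3 says that AUC0-120 "is calculated using Trapezoidal rule from" time 0 to 120 minutes. Neither definition has a baseline term, and no corrected table or listing is planned.

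Protocol 10.2.1 schedules two pre-dose PK samples. On the first: "A first baseline PK blood sample should be collected at the point that plasma glucose first reaches a concentration" below 80 mg/dL. The second comes at the confirmatory glucose reading five minutes later: "collect a second baseline PK blood sample, and begin administration of the study drug".

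Appendix II gives these samples limited work. The 0-minute value is the first point of the AUC. Under section 3.1, if that value "is missing, then PK at -5 minute will be substituted". Section 3.2 averages two draws made at time 0, which again only sets the starting point.

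For glucose, by contrast, SAP 2.4.2 plans a baseline-adjusted AUC0-90 "with negative values set at 0 will also be calculated".

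**The concern.** Protocol 6.1.1 describes glucagon as a pancreatic hormone. Protocol 6.2 states that "The 29 amino acid sequence of pancreatic glucagon is identical in humans, cows, pigs, dogs, and rats" and that the synthetic product keeps this sequence. The documents describe no assay or rule that separates administered from endogenous glucagon, so as written the measured concentration is the sum of the two.

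The stated secondary objective is the pharmacokinetics of G-Pen in each age group. An uncorrected Cmax or AUC answers a slightly different question: how much glucagon of any origin circulated. A persisting endogenous level would add to every value and would vary between children for reasons unrelated to the drug. In the adolescents, who receive both doses, it would add about the same amount to each column of the table and so draw the two columns together in relative terms.

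The baseline samples needed to examine this are already scheduled, in children whose total blood draw is capped at 5% of blood volume (Protocol 11.1).

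**Working it through.** **Is there a figure to reproduce?** No. The documents state no glucagon concentration, Cmax, AUC or dose ratio. Only the direction follows from them; every size below is an assumption.

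**Set-up.** Let E be the drug-derived value at 0.5 mg, R×E the value at 1 mg in the same adolescents, and b a constant endogenous level that persists after dosing. Put f = b/E.

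- Overstatement at 0.5 mg: f
- Overstatement at 1 mg: f/R
- Ratio read across the two columns: (R + f)/(1 + f), which is below R whenever b > 0 and R > 1

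**Cmax, taking R = 2 and f from 1% to 20%:**

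| f | 0.5 mg overstated by | 1 mg overstated by | Ratio read |
|---|---|---|---|
| 0.01 | 1% | 0.5% | 2.01/1.01 = 1.99 |
| 0.05 | 5% | 2.5% | 2.05/1.05 = 1.95 |
| 0.10 | 10% | 5% | 2.10/1.10 = 1.91 |
| 0.20 | 20% | 10% | 2.20/1.20 = 1.83 |

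The same table holds for AUC if f is taken relative to the mean drug-derived concentration over 0 to 120 minutes.

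**AUC when b is stated relative to Cmax.** The endogenous area is 120×b, so the overstatement is 120×b/AUC(drug). The mean concentration over the window is below the peak, so the same b weighs more in AUC than in Cmax. To show how much, I used one-compartment absorption curves at the protocol's sampling times from 0 to 120 minutes, scaled to a peak of 1, with assumed rate constants per minute (ka, ke) of (0.03, 0.02), (0.05, 0.03) and (0.10, 0.03). Their trapezoidal areas are 87.8, 67.6 and 53.5. For b at 10% of Cmax, the overstatement at 0.5 mg is 12/87.8 = 13.7%, 12/67.6 = 17.7% and 12/53.5 = 22.4%. Over the range:

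| b/Cmax at 0.5 mg | AUC at 0.5 mg overstated by | AUC ratio read (true 2.00) |
|---|---|---|
| 1% | 1.4% to 2.2% | 1.99 to 1.98 |
| 5% | 6.8% to 11.2% | 1.94 to 1.90 |
| 10% | 13.7% to 22.4% | 1.88 to 1.82 |
| 20% | 27.3% to 44.8% | 1.79 to 1.69 |

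These curves are illustrations, not estimates for G-Pen.

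**What subtraction does.** If b is constant, subtracting it returns E, R×E and R exactly. Tmax is unaffected by a constant baseline. If endogenous secretion instead stops after dosing, nothing endogenous remains at the peak, and subtracting b makes the Cmax ratio (2 − f)/(1 − f). For f = 0.05, 0.10 and 0.20 that is 2.05, 2.11 and 2.25, an error in the other direction.

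**The case against.** The strongest reply is that the effect may not matter. No baseline level is given, and Protocol 6.1.2 says that glucagon responses to low glucose are often reduced or absent in diabetes. That stands as a reason to doubt the size. It does not establish a zero basal level, because it describes a response to hypoglycemia.

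Second, a reader might infer that the plan will report a compressed dose ratio. It will not. Appendix II section 4 plans means, standard deviations, medians and ranges by age and dose, with no ratio and no dose-proportionality or bioequivalence test. The comparison could only be read by eye across two columns.

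Third, a reader might infer that all the 0.5 mg cohorts are inflated more than the 1 mg cohort. That does not follow. Proportional inflation depends on the drug concentration reached, not on the nominal dose, and the younger children differ from the adolescents in body size. The argument holds only for the two adolescent columns.

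Fourth, SAP 1.2.2 and 2.4.1 call the endpoint serum glucagon, and the mock tables are headed simply as glucagon. Uncorrected values are valid for that quantity. This stands, and it makes part of the point a labelling inconsistency with Appendix II sections 2 and 3.2.1.

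Fifth, glucose Cmax is also taken from the observed profile, and the adjusted glucose AUC is an addition to the raw one. The contrast with PK therefore holds for AUC only, and it supports companion values rather than replacement. Listing 16.2.5.1 would also print each child's pre-dose values, so the baseline is visible though not summarized.

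Finally, subtraction has its own bias. Baseline is drawn at induced low-normal glucose and glucose is then expected to rise, so constant secretion cannot be assumed. This is a sound reason not to make corrected values the only headline.

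**Conclusion.** The gap is certain on the text: exposure is defined as that of G-Pen glucagon, two baseline samples are drawn, and neither is subtracted. The consequence is conditional. If endogenous glucagon is above zero and persists after dosing, raw Cmax and AUC0-120 exceed the drug-derived values, AUC proportionally more, and the adolescent 1 mg and 0.5 mg columns look closer than they should.

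The size cannot be derived from the documents. With baseline assumed at 1% to 20% of the drug-derived value at 0.5 mg, a true ratio of 2.00 reads as 1.99 to 1.83. On the illustrative curves, with baseline set relative to Cmax, the AUC ratio reads as 1.99 to 1.69. At the low end the effect is negligible.

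The flat statement that exposure is overstated is not supported, because it needs a baseline level that the documents do not give. PK is a descriptive secondary endpoint, and the primary glucose analysis is untouched. This is a cheap improvement in how the plan meets its own PK objective, not a flaw in its main conclusion.

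**What to change.** In SAP Appendix II section 3.2, add baseline-corrected Cmax and AUC0-120 as companions to the uncorrected values:

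- Subtract the mean of the -5 and 0 minute concentrations, or the one available.
- Set negative corrected values to 0, as SAP 2.4.2 does for the baseline-adjusted glucose AUC.
- Do not compute corrected values if both pre-dose samples are missing. The section 3.1 rule that imputes time 0 from later samples should not supply a baseline.

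Show both versions in Tables 14.2.1.1 and 14.2.1.3, and add a summary of baseline glucagon by cohort so that a reader can judge whether the correction matters. Label the uncorrected values as total serum or plasma glucagon throughout. State that subtraction assumes constant endogenous secretion and over-corrects if secretion falls.

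The cost is a few lines of SAP text and programming, with no extra blood and no change to the primary analysis.

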3.2.2 T_{Max}

T_{Max} is defined as time (min) when maximum concentration of G-Pen Glucagon reached after T_0 . If there are multiple C_{Max} following the injection, T_{Max} will be the first time when C_{Max} is reached. Actual time instead of protocol time will be used.

3.2.3 $AUC_{0-120min}$

$AUC_{0-120min}$ is calculated using Trapezoidal rule from T_0 to T_{120} . Actual time instead of protocol time will be used.

4 Statistical Analysis

The three PK variables defined in section 3.2 will be analyzed descriptive for the age groups and doses (2.0-<6.0yr 0.5mg, 6.0-<12.0yr 0.5mg, 12.0-<18.0yr 1mg, and 12.0-<18.0yr 0.5mg). Mean, standard deviation, median, minimum and maximum will be presented.

Individual figures of each subject each dose will be presented. Mean G-Pen Glucagon vs protocol time point will be presented for each age group and doses. Protocol time point will be used to allow aggregation.

5 Planned Output Table of Content

Tables	14.2.1.1	Glucagon : Cmax by age and dose
	14.2.1.2	Glucagon : Tmax by age and dose
	14.2.1.3	Glucagon : AUC0-120 by age and dose
Listing	16.2.5.1	PK profile for each subject
	16.2.5.2	PK Cmax, Tmax, AUC for each subject
Figure	14.4.1.1.subjid	Individual Glucagon profile of each subject
	14.4.1.2	average Glucagon vs time for each age group and dose

6 Mock-ups Tables/Listings/Figures
Table 14.2.1.1 Glucagon: Cmax by age and dose

CATEGORY	Glucagon: Cmax			
	2-6yr 0.5mg	6-12yr 0.5mg	12-18yr 1mg	12-18yr 0.5mg
N	6	6	6	6
Mean (SD)	x.x (x.xx)	x.x (x.xx)	x.x (x.xx)	x.x (x.xx)
Min, Median, Max	x.x (x.xx)	x.x (x.xx)	x.x (x.xx)	x.x (x.xx)

Table 14.2.1.2 Glucagon: Tmax by age and dose

CATEGORY	Glucagon: Tmax			
	2-6yr 0.5mg	6-12yr 0.5mg	12-18yr 1mg	12-18yr 0.5mg
N	6	6	6	6
Mean (SD)	x.x (x.xx)	x.x (x.xx)	x.x (x.xx)	x.x (x.xx)
Min, Median, Max	x.x (x.xx)	x.x (x.xx)	x.x (x.xx)	x.x (x.xx)

Table 14.2.1.3 Glucagon: AUC0-120 by age and dose

CATEGORY	Glucagon: Auc0-120			
	2-6yr 0.5mg	6-12yr 0.5mg	12-18yr 1mg	12-18yr 0.5mg
N	6	6	6	6
Mean (SD)	x.x (x.xx)	x.x (x.xx)	x.x (x.xx)	x.x (x.xx)
Min, Median, Max	x.x (x.xx)	x.x (x.xx)	x.x (x.xx)	x.x (x.xx)

Listing 16.2.5.1 Glucagon of each subject

PATIENT ID	Actual Date/Time	Protocol Time	Glucagon
xxxx	xx/xx/yyyy xx:xx	-5	xx
xxxx	xx/xx/yyyy xx:xx	0	xx
xxxx	xx/xx/yyyy xx:xx	10	xx
xxxx	xx/xx/yyyy xx:xx	20	xx

Listing 16.2.5.2 Glucagon Cmax, TMax, AUC of each subject

PATIENT ID	CMax	TMax	AUC01-20
XXXX	XX	XX	XX
XXXX	XX	XX	XX
XXXX	XX	XX	XX
XXXX	XX	XX	XX

[figure not shown]
Figure 14.4.1.1.xxxx Glucagon at each time points

Figure 14.4.1.2 Mean Glucagon at each time points for age/dose group
